Healthy males and females (of non-childbearing potential) between 18 and 55 years of age (inclusive) with total body weight between 50 to 100 kg (inclusive) and body mass index (BMI) between 18.5 and 29.9 kg/m² (inclusive) at the time of the Screening examination.

Investigational Medicinal Product: dose/mode of administration/ dosing schedule:

Tepotinib film-coated tablet (Tablet Formulation 2, TF2) containing 500 mg of drug substance, oral administration.

Omeprazole, 40 mg gastro-resistant hard capsule.

Treatment A: A single oral dose of 500 mg tepotinib will be administered on Day 1 together with 240 mL still water at 30 minutes (min) after start of the breakfast which will have to be consumed completely within 25 min.

Treatment B: Single doses of 40 mg omeprazole will be administered in the fasted state in the morning of Days 1 to 5. In the morning of Day 5, also a single oral dose of 500 mg tepotinib will be administered, in **fasted state**, 2 h after the omeprazole administration.

Treatment C: Single doses of 40 mg omeprazole will be administered in the fasted state in the morning of Days 1 to 5. In the morning of Day 5, also a single oral dose of 500 mg tepotinib will be administered in a **fed state**, 2 h after the omeprazole administration and 30 min after start of breakfast.

Reference therapy: dose/mode of administration/dosing schedule: Not applicable

Planned trial and treatment duration per subject:

About 2 months from Screening to End of Trial Visit, treatment on Day 1 of Treatment A and Days 1 to 5 of Treatments B and C.

Statistical methods:

A linear model with TREATMENT, PERIOD, SEQUENCE and SUBJECT (SEQUENCE) as fixed effects will be applied to log-transformed PK parameters C_{max} , AUC_{0-t} , and $AUC_{0-\infty}$ based on the PK analysis set. Treatment differences C-A and C-B on the log scale will be estimated for C_{max} , AUC_{0-t} , and $AUC_{0-\infty}$ together with their 90% confidence intervals (CIs). Point estimates and CIs will be back-transformed to the original scale.

The relative bioavailabilities C/A and C/B will be calculated for each subject.

Summary statistics will be provided for all parameters.

Table 1 Schedule of Assessments - Screening and End of Trial Visit

Assessment / Activity	Screening	End of Trial Visit
Day	-21 to -2	7 (\pm 1) days after last drug administration in the final period
Written informed consent ^a		
Ambulatory visits	X	X
In-/exclusion criteria	X	

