3.1 Trial Rationale

The impact of the proton pump inhibitor omeprazole on the bioavailability of tepotinib will be studied as the solubility of tepotinib is pH dependent, specifically tepotinib is slightly soluble at pH 4.5 whereas it is practically insoluble at pH 1.2, 6.8, and 7.4 (see [Figure 1](#)). In this study, the impact of the proton pump inhibitor omeprazole on the bioavailability of tepotinib will be studied. A 3-period, crossover study design will be used to investigate the effect of omeprazole on the PK of tepotinib under fasted and fed condition, and based on the regulatory guidelines of the Food and Drug Administration (FDA) [3] and the European Medicines Agency (EMA) [4].

Based to the known minor, but positive food effect on tepotinib exposure (EMR200095-003, see Tepotinib Investigator's Brochure), tepotinib is developed in clinical studies with patients by administration under fed condition. Therefore, the PK of tepotinib after single dose administration under fed condition (Treatment A) will serve as reference in this study.

Figure 1 pH Dependent Solubility Profile of Tepotinib

Source: Analytical Report Re100004.

Data of 2 different batches are presented.

This clinical trial will be conducted in compliance with the clinical trial protocol, ICH GCP and any additional applicable regulatory requirements.

Based on the available nonclinical and clinical data to date, the conduct of the trial specified in this protocol is considered justifiable.

4 Trial Objectives

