4.2 Secondary Objectives

- To investigate the effect of food on the single dose PK of tepotinib after co-administration of omeprazole and tepotinib
- To assess the safety and tolerability of tepotinib alone and upon co-administration of omeprazole.

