5.1 Overall Trial Design and Plan

This is a Phase I, open-label, 3-period, crossover study to investigate the effect of omeprazole on the PK of tepotinib in 12 healthy subjects under fasted and fed condition. A flowchart summarizing the overall study design is shown in [Figure 2](#). Two subjects each will be randomized to one of the six possible treatment sequences.

The study will be divided into 3 periods: in one period, the PK of tepotinib will be evaluated after single dose administration under fed condition (Treatment A), and in two periods omeprazole will be administered for 5 days and a respective single dose of tepotinib will be co-administered on Day 5. Thereby tepotinib will be administered 2 hours after omeprazole administration once under fasted (Treatment B) and once under fed conditions (Treatment C). The washout period will be at least 14 days between tepotinib single dose administrations (see [Figure 2](#)). Subjects will be randomized to one of six possible treatment sequences as detailed in Section 8.2.

Figure 2 Study Design, Exemplified for Sequence 1

Sequence 1	Treatment A				WO ^a	Treatment B				WO ^a	Treatment C					
	Day					Day					Day					
Procedure	-1	1	2 - 4	5 - 7		-1	1 - 4	5	6 - 8	9 - 11		-1	1 - 4	5	6 - 8	9 - 11
Tepotinib administration		↑						↑					↑			
Omeprazole administration						↑↑↑↑↑		↑				↑↑↑↑↑	↑			
PK blood sampling		↔					↔					↔				
Safety assessments ^b	↔				↑		↔				↑		↔			
AE monitoring	↔															
Hospitalization	↔					↔					↔					

Treatment A = tepotinib alone fed; Treatment B = tepotinib fasted with omeprazole; Treatment C = tepotinib fed with omeprazole

a: WO = washout; the washout period will be at least 14 days between tepotinib single dose administrations.

b: Safety assessments: Vital signs, 12-lead ECG, clinical laboratory.

A screening period will occur from Day -21 to Day -2.

Subjects will be admitted to the study site on Day -1 of each period. After administration of tepotinib alone the subjects will be resident at the study site under medical supervision from Days -1 to 4 and must visit the site on the morning of Days 5 to 7 for further blood sampling. In both periods with omeprazole co-administration the subjects will be resident at the study site under medical supervision from Days -1 to 8 and must visit the site on the morning of Days 9 to 11 for further blood sampling.

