8.5.2 Analysis of Primary Endpoint

A linear model with TREATMENT, PERIOD, SEQUENCE and SUBJECT(SEQUENCE) as fixed effects will be applied to log-transformed PK parameters C_{max} , AUC_{0-t} , and $AUC_{0-\infty}$ based on the PK analysis set. Treatment differences C-A and C-B on the log scale will be estimated for C_{max} , AUC_{0-t} , and $AUC_{0-\infty}$ together with their 90% CIs. Point estimates and CIs will be back-transformed to the original scale.

The relative bioavailabilities C/A and C/B will be calculated for each subject and summarized.

Graphical displays will be given, where appropriate. Details of the statistical analysis will be described in the SAP.

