## Changes to the Planned Analyses in the Clinical Trial Protocol

The statistical methods as described in the protocol were adopted.

# 8

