### **16.1.2 Secondary Endpoints**

The effect of food on the single dose PK of tepotinib after co-administration of omeprazole and tepotinib will be investigated by comparing treatments B and C using the linear model described above in 16.1.1, again applied to log-transformed  $C_{max}$ ,  $AUC_{0-t}$ , and  $AUC_{0-\infty}$  of tepotinib.  $C_{max}$ ,  $AUC_{0-t}$ , and  $AUC_{0-\infty}$  of tepotinib under treatment B will be summarized together with treatments A and C in one table. The scatterplots for treatment B will be included in the scatterplots produced for the primary endpoints (16.1.1)

The relative bioavailabilities C/B and C/A will be calculated for each subject and summarized.

Summary statistics will also be provided for  $t_{max}$ ,  $t_{1/2}$ ,  $t_{lag}$ ,  $CL/f$  and  $Vz/f$  of tepotinib (all treatments). For  $t_{max}$ , the Hodges-Lehmann shift estimates will be given for C-B and C-A together with the 90% confidence intervals according to Tukey. PK variables will be evaluated for all subjects of the PK population, but listed for all subjects with available data.

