$F_{\text{rel,C/A}}$	Relative bioavailability (Test versus Reference), defined as $AUC_{0-\infty,C}/AUC_{0-\infty,A}$ and $AUC_{0-\infty,B}/AUC_{0-\infty,A}$ , where $AUC_{0-\infty,C}$ is $AUC_{0-\infty}$ under co-administration of omeprazole under fed conditions, $AUC_{0-\infty,B}$ is $AUC_{0-\infty}$ under co-administration of omeprazole under fasted conditions and $AUC_{0-\infty,A}$ is $AUC_{0-\infty}$ for tepotinib alone und fed condition.
$F = \frac{AUC_{0-\infty \text{ test}}}{AUC_{0-\infty \text{ reference}}} * 100$	

Individual PK parameters will be calculated using actual sampling times. The predose sample will be considered as if it had been taken simultaneously with the administration of study drug. PK variables will be evaluated and listed for all subjects who provide sufficient concentration-time data.

Plasma concentrations below LLOQ before the last quantifiable data point will be taken as zero for calculating the AUC (ie embedded below the limit of quantitation values set to zero). Plasma concentrations below LLOQ after the last quantifiable data point will not be considered for the determination of  $\lambda_z$ .

The following PK parameters will be calculated for diagnostic purposes and listed, but will not be summarized:

- The time interval (h) of the log-linear regression ( $\lambda_{z\ low}$ ,  $\lambda_{z\ upp}$ ) to determine  $\lambda_z$ .
- Number of data points included in the log-linear regression analysis to determine  $\lambda_z$ .
- Goodness of fit statistic (Rsq) for calculation of  $\lambda_z$ .

The regression analysis should contain data from at least 3 different time points in the terminal phase consistent with the assessment of a straight line on the log-transformed scale. Phoenix WinNonlin best fit methodology will be used as standard. The last quantifiable concentration should always be included in the regression analysis, while the concentration at  $t_{max}$  and any <LLOQ concentrations that occur after the last quantifiable data point should not be used.

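### SAP Table 1 defines per-subject relative bioavailability as C/A and B/A, but the protocol and SAP 16.1.2 plan C/A and C/B for tepotinib

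*SAP*

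**What the plan says.** Three places name the per-subject ratios for tepotinib, and they agree:

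- Protocol synopsis, statistical methods: "The relative bioavailabilities C/A and C/B will be calculated for each subject".
- Protocol 8.5.2: "The relative bioavailabilities C/A and C/B will be calculated for each subject and summarized".
- SAP 16.1.2: "The relative bioavailabilities C/B and C/A will be calculated for each subject and summarized".

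For the metabolites, SAP 16.1.3 plans C/A only.

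The one place that writes the ratios out in AUC terms is the relative bioavailability row of Table 1 in SAP 16.1.5. It reads "Relative bioavailability (Test versus Reference), defined as $AUC_{0-\infty,C}/AUC_{0-\infty,A}$ and $AUC_{0-\infty,B}/AUC_{0-\infty,A", then says in words what the C, B and A terms stand for and gives a general formula of test over reference times 100.

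SAP section 7 reports no departure from the protocol: "The statistical methods as described in the protocol were adopted".

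**The concern.** Table 1 lists the parameters to be calculated, so it is the natural source for whoever derives them. Its row contains a ratio that no analysis section asks for (B/A) and omits one that both documents ask for (C/B).

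The two are not interchangeable. The secondary objective is "To investigate the effect of food on the single dose PK of tepotinib after co-administration of omeprazole and tepotinib", which is a comparison of C with B. If B/A were produced and taken for the food ratio, it would mislead in two ways: it also carries the omeprazole effect, and it puts the fasted treatment in the numerator, so it points the opposite way from C/B.

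**Working it through.** The plan gives no figure to reproduce. The check is a comparison of the texts followed by algebra.

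**1. Ratios by location (tepotinib)**

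| Location | C/A | C/B | B/A |
|---|---|---|---|
| Protocol synopsis | yes | yes | no |
| Protocol 8.5.2 | yes | yes | no |
| SAP 16.1.2 | yes | yes | no |
| SAP 16.1.5, Table 1 | yes | no | yes |

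The model contrasts in Protocol 8.5.2 (C-A and C-B), and the comparisons of C with A in SAP 16.1.1 and of B with C in SAP 16.1.2, follow the same pattern as the first three rows.

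**2. What each ratio changes.** The legend to Protocol Figure 2 gives "Treatment A = tepotinib alone fed; Treatment B = tepotinib fasted with omeprazole; Treatment C = tepotinib fed with omeprazole".

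- C/A: both fed; omeprazole added. This is the omeprazole effect.
- C/B: both with omeprazole; fed against fasted. This is the food effect.
- B/A: omeprazole added and fed changed to fasted. Both factors move together.

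**3. Algebra.** Within a subject, B/A = (C/A) / (C/B), so C/B = (C/A) / (B/A). B/A fixes the food ratio only when C/A is also known.

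**4. Illustration with assumed values.** Protocol 3.1 calls the food effect minor but positive and gives no size. Take C/B = 1.25 as an assumption. For C/A use the test/reference ratios of Protocol Table 7 (0.50, 0.75, 1.25, 1.50), plus 1.00 for no omeprazole effect.

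| C/A | B/A = (C/A)/1.25 | On the SAP percentage scale |
|---|---|---|
| 0.50 | 0.40 | 40% |
| 0.75 | 0.60 | 60% |
| 1.00 | 0.80 | 80% |
| 1.25 | 1.00 | 100% |
| 1.50 | 1.20 | 120% |

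The food ratio is the same in every line. At C/A = 1.25, B/A shows no difference although food changes exposure by 25%. Only at C/A = 1.00 is B/A the plain inverse of the food ratio (1/1.25 = 0.80).

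**5. Count.** 12 planned subjects × 1 ratio on AUC0-∞ = at most 12 B/A values, against at most 12 planned C/B values. There would be fewer if the SAP 16.1 rule that drops AUC0-∞ from descriptive statistics when the extrapolated part exceeds 20% is carried through to the ratios.

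**The case against.** The strongest reply is that nothing planned is lost. SAP 16.1.2 names C/B explicitly, the general formula in the Table 1 row is enough to compute it, and the row does not say that its two ratios are the only ones. On that reading the likely result is an extra B/A column. The analysis is descriptive with no hypothesis tests, the model-based estimates do not use these ratios, and the row itself says what A and B are, so a careful reader would not take B/A for a food ratio. B/A also has a visible origin: Protocol 3.1 says "Therefore, the PK of tepotinib after single dose administration under fed condition (Treatment A) will serve as reference in this study", and Protocol 3.1 and 5.1 describe the study as examining omeprazole under both fasted and fed conditions.

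Much of this stands. The effect is limited to a descriptive summary, B/A may well appear beside C/B, and the values in the illustration are assumptions: Table 7 lists precision scenarios, not expected effects.

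It does not remove the conflict. The row specifies which ratios it means, and C/B is not one of them. Having A as the study reference may explain how B/A arose, but it does not plan B/A in any analysis section. Recovering C/B as (C/A)/(B/A) needs a usable A value, so a subject with valid B and C but no valid A would have a direct C/B and no recoverable one. Nor can the arithmetic mean or median of C/B in general be rebuilt from summaries of the other two ratios.

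**Conclusion.** The concern holds. The Table 1 row contradicts the protocol synopsis, Protocol 8.5.2 and SAP 16.1.2, and SAP section 7 declares no change that would account for it. A ratio mixing the omeprazole and food effects is defined, and the planned food ratio is not.

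The reach is small: one descriptive output, at most 12 values, assuming 12 complete subjects and one ratio per comparison on AUC0-∞, the only parameter the row names. The estimates and 90% confidence intervals for C against A and C against B are unaffected. It should still be corrected, because the output is planned in both documents and bears on a stated secondary objective. The conclusion rests on the definition text of the row, which is complete; I make no point of the symbol in the left-hand column, and none about the metabolites.

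**What to change.** In SAP Table 1, replace the row with two, each with its own symbol:

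- F_rel,C/A = AUC0-∞,C / AUC0-∞,A (test C, reference A; omeprazole effect when fed), for tepotinib under 16.1.2 and for the metabolites under 16.1.3.
- F_rel,C/B = AUC0-∞,C / AUC0-∞,B (test C, reference B; food effect under omeprazole), for tepotinib under 16.1.2.

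Delete B/A. If it is wanted, keep it as a separately labelled addition declared in SAP section 7, with a note that it isolates neither the food effect nor the omeprazole effect.

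The cost is one table row split into two, plus one sentence in section 7 if B/A stays. The protocol, the data collected, the subjects and the sample size do not change.

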## 16.2 Pharmacogenetics

The results of the pharmacogenetic analysis, as applicable, will be described in a separate report.

17 References

None.

18 Appendices

None.
